6.1 Study Design and Procedures

6.2 Dimensions of the RE-AIM framework

The overall aim of this study is to assess the feasibility and efficacy of the community-based CRC screening intervention in increasing CRC screening rates. We have designed this controlled trial in an effort to improve the quality of CRC screening that people receive and to assess whether or not implementing a community-based intervention where FIT tests are dispensed by community stakeholder will increase screening rates for CRC in specific community areas in

Chicago. If we find evidence supporting the efficacy of our intervention, that will demonstrate that community-based CRC screening interventions that actively involve community stakeholders in screening education and implementation may be a potential tool to improve health outcomes among the people that live in medically underserved communities. The RE-AIM framework will be used to evaluate both process and outcomes of the intervention program (Gaglio et al. 2013; Glasgow et al. 1999; Glasgow et al. 2019). The RE-AIM framework has proven utility in assessing program impact. Through the RE-AIM Framework we will be able to assess Reach, Effectiveness, Adoption, Implementation and Maintenance.

Data will be collected to evaluate our ability to “reach” targeted community members, hard to reach community members and the targeted number of participants. This is defined as the absolute number, proportion, and representativeness of individuals who are willing to participate in screening within our target community area. The clinical outcomes proposed through this project include improved screening of high risk populations for CRC screening and improved early detection of cancer through improved screening. To disseminate the findings to key stakeholders and community members, we will hold town hall forums to inform community members of findings from the project and produce infographics that clearly and succinctly communicate study findings.

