3.0 Objectives/Aims

We propose to address the multiple determinants of health that impact CRC screening in the South Shore community in the UI Cancer Center's catchment area by conducting a quasi-experimental intervention to test the effectiveness of FIT tests dispensed by community stakeholders (community-dispensed) versus FIT tests dispensed using standard of care procedures by a clinic (clinic-dispensed) on FIT test return rates. This

study will follow ACS guidelines for FIT testing, with the South Shore community area assigned to the intervention group (community-dispensed). CRC screening within the Mile Square Englewood Health Center, using standard of care, will serve as our control group to use for comparison (clinic-dispensed). The intervention will include a multifaceted approach to health education and community engagement focused on CRC led by a team of trusted health champions (community leaders, a barber, a hair salon, and community health workers) in the South Shore community area. We specifically propose to investigate the following three specific aims to be achieved over the three-year project period:

Aim 1: To assess the feasibility and efficacy of the community-based CRC screening intervention in increasing CRC screening rates;

Aim 2: To evaluate individual-level knowledge related to CRC screening and risk factors;

Aim 3: To characterize individual -level facilitators and barriers to engaging in CRC screening and related diagnostic tests and treatment when applicable.

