4.1 Eligibility

Community Intervention Group/Arm

Eligibility to participate in this community intervention will primarily be driven by location of residence and age, since screening CRC have established age criteria for screening initiation. A total of four community health navigators will be deployed in the South Shore community area. Each navigator will be trained to understand the eligibility criteria and determine subject eligibility. For those that consent to take the FIT kit and return it, the navigator will document the participants' eligibility in the appropriate REDCap participant information form (attached).

Standard of Care Comparison Group/Control Arm

Within the Mile Square Health Center system, lay navigators already work to do colorectal cancer screening in the Mile Square Health Center setting. It is standard of care for these navigators to engage patients in health education and awareness regarding the need for colorectal cancer screening. As such, each navigator is familiar with eligibility criteria for screening under standard of care. For the purposes of this study, we will use deidentified aggregate data from the CRC screening navigation program at the Mile Square Health Center in Englewood as a comparison group to evaluate the value of the community intervention relative to standard of care. As general practice, each navigator at MSHC keeps a running tally of the number of patients approached, deemed eligible, and who opt to participate in colorectal cancer screening during each day the navigator works in the health center setting.

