4.3 Exclusion Criteria

- Adults ages <45 or >74, those that do not speak English, do not reside in or near the South Shore community area, do not utilize the Mile Square Englewood Health Center, or have had CRC screening in the previous 12 months.

Table 1. Inclusion and Exclusion Criteria

Cancer Screening	4.1 Inclusion Criteria	4.2 Exclusion Criteria
Colorectal	Male or Female Age ≥45 and < 75 years Resides in or near the South Shore community area (within UI Health MSHC-South Shore Clinic Service Area) Utilizes the Mile Square Englewood Health Center	Age <45 or >75 years Does not reside in or near the South Shore community area (within UI Health MSHC- South Shore Clinic Service Area) Does not utilize the Mile Square Englewood Health Center Does not speak English Has received CRC screening in past 12 months

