For the standard of care control arm, we will obtain deidentified aggregate data from the Mile Square Englewood patients that are approached following standard practice utilizing clinic schedules, walk-ins, etc. to identify potentially eligible participants for CRC screening during the intervention period. This aggregate data will include the number approached, the number eligible, the number that take and return the FIT kit, and the number of FITs returned. Among those that return the FIT, aggregate data will be provided detailing the proportion of positive FITs, the proportion of positive FIT participants who return for diagnostic services, and the proportion of detected cancers.

Table 2. Subject Enrollment Plan

Screening Target	Community-Based (Intervention Arm)
Colorectal	
 Community navigators will work with local businesses (barber shop, hair salon) to identify and screen eligible community members within or near the South Shore community area. The navigator will engage with each potential participant using the attached script. If the participant is interested, the navigator will document the participant's contact information, and assist the participant in obtaining and returning their FIT. Community navigators will attend community events to post the informational flyer and provide education about CRC to community members. At these events, they will identify and screen eligible community members within or near the South Shore community area. The navigator will engage with each potential participant using the attached script. If the participant is interested, the navigator will document the participant's contact information, and assist the participant in obtaining and returning their FIT.
Screening Target	
 Standard of Care Clinic-Based Comparision Group (Control Arm)

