FITs will be returned via mail directly to the UICC, where they will be processed following the manufacturer's guidelines. Navigators will call back each participant to let them know about the results of their FIT using the attached script. If a participant screens positive, the participant will be informed by the navigator, who will direct the participant to the MSHC- South Shore Clinic, and connect the participant to the MSHC- South Shore clinical patient navigator. We will track the time between FIT dispensing and return, and the time between FIT processing and participant agreement to engage in diagnostic testing with the clinical navigator at MSHC as indicated (for those that screen positive). Once the FIT is returned, participation in the study will end. However, for those that have a positive/abnormal FIT, the community navigator will refer the person to MSHC for clinical follow-up. This is not part of the research, but to ensure a continuum of care among those that screen positive. The clinical navigator will follow the standard clinical flow and standard clinical care practices used at the MSHC- South Shore Clinic to schedule the participant for a diagnostic test, and any further procedures or treatments necessary. This will include, but is not limited to, helping the participant enroll in a health insurance program if the participant is uninsured, and/or obtaining a voucher to pay for the diagnostic/further screening examinations and tests. For CRC screening, we have partnered with administrative and clinical staff at the MSHC- South Shore clinic in the South Shore community area to facilitate this transition when needed.

Standard of Care Comparison Group/Control Arm

For the standard of care control arm, the lay patient navigator at Mile Square Englewood Health Center will provide deidentified aggregate data from the Mile Square Englewood patients that are approached following standard practice utilizing clinic schedules, walk-ins, etc. to identify potentially eligible participants for CRC screening during the intervention period. This aggregate data will include the number approached, the number eligible, the number that take and return the FIT kit, and the number of FITs returned. Among those that return the FIT, aggregate data will be provided detailing the

proportion of positive FITs, the proportion of positive FIT participants who return for diagnostic services, and the proportion of detected cancer.

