9.1 Data Analysis

- Prior to any analyses, all data sources (tracking, demographic, and questionnaire) will be cleaned and linked using the participant unique study identifier. We will summarize the data using frequencies and percentages for categorical variables, and means and standard deviations for continuous variables.

Aim 1: To assess the feasibility and efficacy of conducting a community-based CRC screening intervention in increasing CRC screening rates. We aim to evaluate the feasibility and efficacy of conducting a community-based navigation program for colorectal cancer screening. In both arms of the study, we will examine the number of participants who were provided with health education about colorectal cancer, the number of FITs distributed, and the number of FITs returned. We will summarize the number of persons screened positive and negative, and determine the proportion of positive screening participants who are referred to clinical care overall, and at the Mile Square South Shore and Englewood sites through our community navigation program (intervention) and existing MSHC lay clinical navigation program. We will compare the FIT return rate and average return time at the South Shore and Englewood sites to determine if the rates and times are similar. We will also determine return rates and times for participants who screen positive and are navigated to return the MSHC for diagnostic testing, and make comparisons across the intervention and control arms.

Aim 2: To evaluate individual-level knowledge related to CRC screening and risk factors. We aim to assess knowledge related to CRC screening and risk factors as measured by our short survey that participants will return with their FIT. We will summarize the frequency and percentage of respondents who have had a prior CRC screening, in addition to the frequency and percentage of respondents who select the correct answers on knowledge questions.

Aim 3: To characterize individual -level facilitators and barriers to engaging in CRC screening and related diagnostic tests and treatment when

applicable. We aim to evaluate facilitators and barriers people living in or near the South Shore communities experience related to CRC screening and related follow-up. We will summarize the respondent responses to survey questions about barriers and facilitators.

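### The plan cannot separate added from displaced screening, so a claim that screening rose in South Shore could be overstated by an unknown amount

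*Combined protocol and SAP*

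**What the plan says.** The purpose in section 6.2 is at area level: to learn whether an intervention in which FITs are "dispensed by community stakeholder will increase screening rates for CRC in specific community areas". Aim 1 (sections 3.0 and 9.1) likewise speaks of raising CRC screening rates.

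The effect to be tested is narrower. Section 3.0 sets community-dispensed kits "versus FIT tests dispensed using standard of care procedures by a clinic (clinic-dispensed) on FIT test return rates". Section 9.1 follows this: "We will compare the FIT return rate and average return time at the South Shore and Englewood sites". It adds descriptive counts for both arms: "we will examine the number of participants who were provided with health education about colorectal cancer, the number of FITs distributed", and the number returned.

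The community arm overlaps with a clinic of the same health system. Table 1 (section 4.3) gives the residence criterion as "Resides in or near the South Shore community area (within UI Health MSHC-South Shore Clinic Service Area". Section 4.1 says: "Within the Mile Square Health Center system, lay navigators already work to do colorectal cancer screening in the Mile Square Health Center setting". Under section 6.3, a community navigator will "connect the participant to the MSHC- South Shore clinical patient navigator" when the FIT is positive.

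Clinic data come from one place. In section 5.0, "we will obtain deidentified aggregate data from the Mile Square Englewood patients"; sections 4.1 and 6.3 also name Englewood only. Sections 4.2 and 4.3 exclude anyone screened for CRC in the previous 12 months. No criterion or analysis refers to being an existing clinic patient or to holding a clinic FIT.

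**The concern.** A person in the South Shore service area who is due for a clinic FIT, or already holds one, can take the community kit instead. Section 5.0 offers community participants $25; the clinic procedures in Table 2 mention no incentive. If that person would have completed the clinic test, the community return adds nothing to screening in the area: one test has moved from one route to the other.

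Nothing in the planned data would show this. The clinic that could lose the test is MSHC-South Shore, and its counts are not requested. The problem is separate from whether Englewood is a fair comparator. A perfectly matched Englewood arm would still show only returns per kit dispensed, not whether more South Shore residents were screened.

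At stake is the conclusion that section 6.2 wants to draw. A good return rate could be reported as evidence that screening in South Shore increased when the data cannot support that step.

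**Working it through.** **No plan figure to reproduce.** The documents give an intervention-arm target of at least 600 (section 5.0). They give no expected return rate, effect size, power or South Shore clinic volume. In what follows only 600 comes from the documents; every other value is an assumption.

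**Step 1: what the area-level question needs.** Let N be kits dispensed, r the return rate, and s the share of returners who would otherwise have completed a clinic FIT.

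- Gross community returns = N × r
- Net added screens = N × r × (1 − s)
- Excess of gross over net = s/(1 − s)

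The plan observes N and r. It has no data on s, so a programme with s = 0 and one with s = 0.5 can produce the same data set.

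**Step 2: size under assumed s.** With N = 600 and r = 0.5, gross returns are 600 × 0.5 = 300.

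| s | Net added | Excess of gross over net |
|---|---|---|
| 0 | 300 | 0% |
| 0.1 | 270 | 11% |
| 0.2 | 240 | 25% |
| 0.3 | 210 | 43% |
| 0.5 | 150 | 100% |

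The percentages do not depend on r; they are the same at r = 0.3 and r = 0.7. One way to arrive at s is to multiply the share of returners who are clinic patients by the probability that such a patient would have completed a clinic FIT. Assuming 0.20 × 0.30 = 0.06 displaces 18 of 300; assuming 0.50 × 0.60 = 0.30 displaces 90 of 300. Neither pair has support in the documents, and s = 0 is not ruled out.

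**Step 3: the contrast actually planned.** Let a be the share of the community arm attached to the clinic. The observed return rate is a × r_att + (1 − a) × r_unatt, and s does not appear in it. Take a = 0.3, r_unatt = 0.5 and an Englewood rate of 0.5:

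- r_att = 0.5: 0.15 + 0.35 = 0.50, difference 0
- r_att = 0.7: 0.21 + 0.35 = 0.56, difference +6 points
- r_att = 0.4: 0.12 + 0.35 = 0.47, difference −3 points

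The contrast moves only if attached people return kits at a different rate, and it can move either way.

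**Step 4: do existing provisions supply s?** The 12-month exclusion removes people recently screened. It leaves in those who are due and those holding an unreturned clinic kit, who are the people able to substitute. The prior-screening item in section 9.1 comes from the survey returned with the FIT, so it misses non-returners, and as described it concerns past screening rather than a current offer elsewhere. Registration as an MSHC patient appears only after a positive FIT (section 5.0).

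**Step 5: would counting only people without another FIT offer solve it?** No. Take the two cases in Step 2 and suppose that every attached returner had an offer. The no-offer group is 240 when the net gain is 300 − 18 = 282, and 150 when it is 300 − 90 = 210. The rule would understate the gain by 42/282 = 15% and 60/210 = 29%, because some people with an offer would never have completed it.

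**The case against.** The strongest reply is that the plan estimates no area screening rate and no number of added screens. It compares return rates, and a displaced person enters both numerator and denominator, so displacement alone leaves that comparison unbiased. This stands. A reader might infer that the plan credits each community return as an increase, or that its result is biased in the programme's favour. The documents support neither: section 9.1 contains no such calculation, and Step 3 shows that the direction is undetermined.

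Three further points have weight. The 12-month exclusion is a real safeguard, and because section 2.0 describes FIT screening as annual, it removes many people who are up to date through a clinic. FIT dispensing at MSHC-South Shore is inferred from the system-wide statement in section 4.1: the detailed clinic procedures in Table 2 are Englewood's, and the South Shore navigator appears only in follow-up of positive tests. The Participant Information Form and survey are attachments not shown, so attachment may be collected; only its absence from the eligibility criteria and analysis text can be asserted.

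Finally, the ambition is modest. Section 6.2 speaks of a potential tool, and section 12.1 of informing future interventions. That lowers the stakes, but it does not supply the missing link between a return rate and an area-level increase.

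**Conclusion.** The concern holds as a gap between question and data. Section 6.2 asks about screening in the area, section 9.1 measures returns per kit against another clinic, and nothing collected connects the two. A claim of increased South Shore screening could be overstated by an unknown amount. On assumed displacement shares of 0 to 0.5 the gross count exceeds the net gain by 0% to 100%, and the documents do not narrow that range.

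For that one reading, returns taken as added screening, displacement can only overstate. It would go too far to infer that overstatement has been shown, or that any particular range such as 6% to 30% displaced is likely: the return rate and displacement share are assumed, and zero displacement is compatible with the text. The planned return-rate comparison is not faulted on this ground. The change is worth making because it is cheap and bears directly on the trial's stated question.

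**What to change.** 1. At enrolment, ask everyone given a kit whether they are a current patient of MSHC or another clinic, and whether they were offered or hold a FIT there in the past 12 months. If the Participant Information Form already asks this, name the item in section 9.1. Report kits dispensed and returned by this status as a descriptive split. Do not define added screening as returns from the no-offer group only (Step 5).

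2. Request de-identified aggregate FIT counts, dispensed and returned, from MSHC-South Shore for the study years and the preceding year. Report clinic plus community returns for South Shore next to the Englewood counts. State that a before/after change is descriptive and subject to time trends, and that a modest shift may be hard to see if the clinic's volume is large. These counts will not show displacement from other providers; item 1 gives partial information on that.

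3. If the counts in item 2 cannot be obtained, limit the section 6.2 conclusion to return rates among people given a kit, and make no claim of an area-level increase.

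The cost is one form item, one more aggregate request to a clinic that section 6.3 already names as a partner, and one extra table. The downside is a narrower, or possibly smaller, headline claim. Item 1 is best in place before enrolment, since later recall of clinic offers would be weaker.

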5.0 Subject Recruitment and Enrollment

Participants will have an opportunity to enroll in this project at multiple points as summarized in Table 2. We will enroll at least 600 men and women across a three-year period for CRC screening in the South Shore community area, and acquire deidentified aggregate comparison data for the men and women who engage in CRC screening in the Mile Square Englewood Health Center across the same three-year period.

Community Intervention Group/Arm

For the intervention arm, the team of community navigators will recruit participants from multiple venues. We will work with local business owners who are actively engaged in health advocacy and will use their local businesses as sites of participant recruitment (Cut It Out Curt, a barber shop and a hair salon (Location TBD)) to identify and inform eligible community members within or near the South Shore community area about CRC screening. These partners will post the attached CRC screening flyer, and engage with each potential participant to provide information and education about CRC screening using the attached script. If the participant is interested, the partner will inform one of our trained community navigators who will connect with the interested participant to review the study information sheet and ask the participant to provide written consent to participate. Once the participant agrees to participate, the navigator will document the participant's contact information, and assist the participant in obtaining and understanding how to use and return their FIT via mail. The navigator will also give the participant a short survey (attached) to complete. The FIT test, instructions, survey, and mailing envelope will be contained in a "FIT Kit," a labeled plastic bag, that will be

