dispensed to participant by the community navigator. The FIT and survey will be returned to the UICC via mail or dropped off at the barber or hair salon using a drop box (to be picked up regularly by research personnel), where it will be processed by key research personnel following the manufacturer's instructions. Participants who receive their FIT from the barber or hair salon will be offered a \$25 gift certificate to the barber or hair salon for use towards a future service. Each community navigator will keep a tally of the number of participants who are approached, eligible, and who decline to participate in screening for evaluation purposes. All potential participants will be informed that declining participation will not influence their ability to participate in any future activities at either business or with the UICC.

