In addition to recruitment efforts in the barber shop and beauty salon, our community navigators who are trained on the study protocol will attend community events in the South Shore and surrounding communities such as the annual African Festival of The Arts (<https://www.aihua.org/african-festival-of-the-arts>) where UICC hosts an informational table each year. These navigators will use the attached CRC screening flyer, and engage with each potential participant to provide information and education about CRC screening using the attached script. If the participant is interested, the navigator will review the study information sheet and ask the participant to provide written consent to participate. Once the participant agrees to participate, the navigator will document the participant's contact information, and assist the participant in obtaining and understanding how to use and return their FIT. The navigator will also give the participant a short survey (attached) to complete. The FIT and survey will be returned to the UICC via mail or dropped off at the barber or hair salon using a drop box, where it will be processed following the manufacturer's instructions. Any positive FIT will be promptly reported (within 48 hours) to the MSHC clinical navigator, who will follow standard practices to register the participant as a patient, and navigate the participant through standard medical care if clinical follow-up is needed due to a positive screening and need for a diagnostic examination within the MSHC System. Participants who receive their FIT from a community navigator outside of the barber or hair salon setting will be offered a \$25 incentive (Walgreens store gift card or cash) to be paid upon receipt of the FIT to UICC. Each navigator will keep a tally of the number of participants who are approached, eligible, and who decline to participate in screening for evaluation purposes.

Standard of Care Comparison Group/Control Arm

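### The proportion reached may be overstated in the barber shop and hair salon: the plan conflicts on who approaches customers, and only navigators keep a tally

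*Combined protocol and SAP*

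**What the plan says.** Section 6.2 names the five RE-AIM dimensions but defines only reach: "the absolute number, proportion, and representativeness of individuals who are willing to participate in screening within our target community area".

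For the shop channel, section 5.0 gives the first contact to the business partners: "These partners will post the attached CRC screening flyer, and engage with each potential participant to provide information and education about CRC screening". It continues: "If the participant is interested, the partner will inform one of our trained community navigators who will connect with the interested participant". The record of non-participants belongs to the navigator: "Each community navigator will keep a tally of the number of participants who are approached, eligible, and who decline to participate in screening". No log kept by the partners is described.

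For community events, section 5.0 has the navigator approach people directly and keep the same counts: "Each navigator will keep a tally of the number of participants who are approached, eligible, and who decline to participate in screening".

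Table 2 (section 5.0), in the entry covering the barber shop and salon, describes the approach differently: "The navigator will engage with each potential participant using the attached script". Section 6.3 repeats that sentence for the intervention arm.

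Section 8.1 lists demographic data and full street address among the participant data held, and section 9.1 links demographic data for analysis. Section 9.1 gives no analysis of the reach proportion or of representativeness, and names no reference population.

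**The concern.** A proportion willing to be screened is only as good as its denominator. If the partner makes the first approach and calls the navigator only for interested people, anyone who turns the partner down has no described route into the count. The shop denominator then consists mainly of people who have already shown interest, and the recorded proportion is too high.

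This matters because feasibility is part of the primary aim (section 12.1) and reach is the one RE-AIM dimension with a stated definition. Refusals that nobody writes down cannot be recovered at analysis. Because the sections disagree, an analyst holding the final tallies could not tell which procedure had produced them. A related Aim 1 count in section 9.1, the number of people given health education, has the same weakness: no source is stated for education given by the shop partners.

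**Working it through.** The plan gives no reach figure to reproduce. The enrollment target of at least 600 (section 5.0) has no stated derivation and serves here only as a scale. The result does not depend on it, because 600 cancels in the formula below.

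**Who approaches and who records**

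| Place | First approach | Record of refusals |
|---|---|---|
| 5.0, shop text | Partner; navigator called if the person is interested | Navigator's tally only |
| 5.0, event text | Navigator | Navigator's tally |
| Table 2, shop entry | Navigator | None stated; 5.0 tally would apply |
| 6.3, intervention arm | Navigator | None stated; 5.0 tally would apply |

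The first row loses refusals made to the partner. The other three lose none.

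**Possible size of the distortion**

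Assumed inputs, none of them in the plan:
- p = true proportion accepting among all approached in the intervention arm
- s = share of all decliners who are in the shops
- f = share of shop decliners who refuse at the partner stage and go untallied

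With 600 enrolled:
- decliners D = 600/p − 600
- untallied = f × s × D
- recorded proportion = 600 / (600 + D − f × s × D)

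For p = 40% and s = 50%: approached = 600/0.4 = 1,500, so D = 900, of whom 450 are in shops.
- f = 0: 600/1,500 = 40.0%
- f = 0.5: 225 lost; 600/1,275 = 47.1%
- f = 1: 450 lost; 600/1,050 = 57.1%

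Recorded proportion over a wider range:

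| True p | f = 0, any s | f = 0.5, s = 50% | f = 1, s = 25% | f = 1, s = 50% | f = 1, s = 75% |
|---|---|---|---|---|---|
| 20% | 20.0% | 25.0% | 25.0% | 33.3% | 50.0% |
| 40% | 40.0% | 47.1% | 47.1% | 57.1% | 72.7% |
| 60% | 60.0% | 66.7% | 66.7% | 75.0% | 85.7% |

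The f = 0 column is the procedure in Table 2 and section 6.3. The f = 1 columns are the extreme of the partner-first procedure. Anyone who shows interest and then declines to the navigator is still counted, so f would normally be below 1. These are arm-wide figures; the shop channel taken alone would be distorted more.

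**Representativeness**

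Participants can be compared with an external population without data on decliners. The 95% half-width for a participant share q at n = 600 is 1.96 × √(q(1−q)/600):
- q = 5%: 1.7 percentage points
- q = 25%: 3.5 points
- q = 50%: 4.0 points

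Precision is therefore adequate. What is missing is a named comparator and a list of variables.

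**The case against.** The strongest reply is that the loss of shop refusals is an inference from one paragraph. Table 2 and section 6.3 both put the navigator in front of each potential participant, and the navigator's tally is described within the shop recruitment text itself. No sentence excludes people who refuse the partner. This stands to the extent that zero bias is a legitimate reading. It does not remove the point, because the shop text of section 5.0 is the most detailed account of that channel, and staff who followed it would undercount refusals.

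A reader might go further and infer that shop refusals never enter the tally, or that neither reach nor representativeness can be computed. The documents support neither. Table 2 and section 6.3 contradict the first. On the second, the absolute number is known, the event-channel proportion can be computed, and the definition in section 6.2 refers to the target community area, so comparing participants with that area's population is a natural reading of representativeness. The tally is described only as counts, so participants cannot be compared with decliners, but the definition does not ask for that comparison. The participant information form and survey are attachments not seen here, so the exact demographic fields cannot be checked.

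It is also fair to say that the main comparison concerns FIT return rate and return time (sections 3.0 and 9.1). Untallied refusals do not enter it.

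**Conclusion.** The point holds in limited form. The plan conflicts with itself on who makes the first approach in the shops and describes no partner record. Under the section 5.0 shop text the reach proportion is biased upward in that channel; under Table 2 and section 6.3 it is not. If half of all decliners are in shops, a true 40% would be recorded as anything from 40% to 57%, depending on the share of shop refusals lost. That range rests wholly on assumed inputs and shows direction and scale only. Separately, representativeness is part of the definition but has no planned analysis. This is worth correcting before recruitment because the lost counts cannot be rebuilt. It does not threaten the FIT return comparison.

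**What to change.** 1. Reconcile the shop text of section 5.0 with Table 2 and section 6.3 on who approaches people in the shops and who records the outcome.
2. In section 5.0, have the barber and salon partners keep the same approached, eligible and declined tick sheet as the navigators, by venue. Sex and broad age group of decliners can be optional, and should be treated as approximate.
3. In section 9.1, report reach by venue as consenters divided by those approached and not known to be ineligible. This uses the eligibility information already tallied and keeps in the denominator people who refuse before eligibility is established.
4. In section 9.1, assess representativeness by comparing participants' age, sex and race/ethnicity, as collected, with the age-eligible population of the South Shore area.

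The cost is a revised tick sheet, brief instruction for the shop partners and a small recording burden on them. Eligibility will remain unknown for some refusers, so the denominator will include some ineligible people and reach will be somewhat understated on that account.
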